### 5.2.2. Change from Baseline

Change from baseline will be calculated as post-baseline value – baseline value. If either the baseline or post-baseline value is missing, the change from baseline is set to “missing”.

Percentage change from baseline will be calculated as  $[(\text{Post baseline value} - \text{Baseline value}) / \text{Baseline value}] \times 100$ .

### 5.2.3. Study Day

Study day will be calculated from first dose as:

Study day = date of assessment – date of first dose +1 if the date of assessment is later than the date of first dose; Otherwise Study day = date of assessment – date of first dose.

One cycle corresponds to 28-days, with the first day of treatment designated as Day 1. For subjects who are randomized/enrolled but not dosed, Day 1 will be the randomization/enrollment day.

## 5.3. Missing Data

Missing efficacy data will not be imputed.

### 5.3.1. Handling of Missing Dates/Months/Years for All Adverse Events

If the start/end date of an AE is partially missing, the date will be compared as far as possible with the first dose date of study drug. The AE will be assumed as treatment emergent if it cannot be definitively shown that the AE did not occur or worsen during the treatment-emergent period, from first dose of study drug to 30 days after last dose of study drug (worst case approach).

- Start dates:
  - For missing start day only: Day will be imputed as the first day of the month (i.e., 01) with the following exception: if the partial date falls in the same month and year as first dose date, then the partial date will be imputed to equal first dose date.
  - For missing start day and month: Day and month will be imputed as the first day of the year (i.e., 01 January) with the following exception: if the partial date falls in the same year as first dose date, then the partial date will be imputed to equal first dose date.
  - For missing start day, month, and year: Date will be imputed to the first dose date.

- Imputed start dates must be prior to the discontinuation date or completion date.
- Stop dates:
  - For missing stop day only: Day will be imputed as the last day of the month (i.e., 28, 29, 30, or 31).
  - For missing stop day and month: Day and month will be imputed as the last day of the year (i.e., 31 December).
  - For missing stop day, year, and month: Date will be imputed as date of discontinuation or completion.
  - Imputed dates should not extend beyond the date of completion or discontinuation.
  - Imputed stop dates must be on or after the start date.

### **5.3.2. Handling of Missing Dates/Months/Years for Concomitant Medications**

Prior or concomitant medications with incomplete dates will be handled as follows for the sole purpose of determining whether a non-study medication is a concomitant medication. If the start/stop date of a medication is partially missing, the date will be compared as far as possible with the first dose date of study drug and the medication will be assumed as concomitant if it cannot be definitively shown that the stop date is before the start of administration of study drug, or the start date is after the last visit of the study.

- If the start and stop dates are both completely missing, a medication will be considered concomitant.
- Start date:
  - For missing start day only: Day will be imputed as the first day of the month (i.e., 01).
  - For missing start day and month: Day and month will be imputed as the first day of the year (i.e., 01 January).
  - Missing start dates will not be imputed.
- Stop date:
  - For missing stop day only: Day will be imputed as the last day of the month (i.e., 28, 29, 30, or 31).
  - For missing stop day and month: Day and month will be imputed as the last day of the year (i.e., 31DEC).
  - Imputed stop dates must be on or after the start date.

The original partial or missing date will be shown in listings of all non-study medications.

### **5.4. Visit Windows**

For study assessment days, there is  $\pm 3$ -day window allowable for each clinic visit during Cycle 1. For Cycles 2 through 25, the allowable window is  $\pm 7$  days. After Cycle 25, the allowable window is  $\pm 1$  month for each clinic visit and its associated assessments.

There is no plan to re-assign visits based on actual visit dates. The analysis will be based nominal visit/time points collected.

## 5.5. Subgroups

- Tumor bulk (largest lymphoid mass <5 cm vs. ≥5 cm)
- Tumor bulk (largest lymphoid mass <7 cm vs. ≥7 cm)
- Prior use of lenalidomide in combination of rituximab (yes vs. no)
- Disease response to last therapy (relapse vs. refractory)
- Disease response to prior anti-CD monoclonal antibodies (relapse vs. refractory)
- Disease response to prior alkylating agents (relapse vs. refractory)
- Disease response to prior bendamustine (relapse vs. refractory)
- Disease response to prior immunochemotherapy (relapse vs. refractory)
- Number of prior lines of systemic cancer treatments (2 vs. >2)
- Number of prior lines of chemo regimens (1, 2-3, 4+)
- PD within 24 months of first line immunochemotherapy (POD24) (yes vs. no)
- Age (<65 vs. ≥65)
- Sex (Male vs. Female)
- Region (North America, Europe, Asia-Pacific)
- Race (Caucasian, Black, Asian, Other)
- Baseline Eastern Cooperative Oncology Group (ECOG) (0 vs. ≥1)
- Disease stage at diagnosis (1-2 vs 3-4)
- Disease stage at study enrollment (1-2 vs 3-4)
- Duration of treatment-free interval from the last lymphoma-directed therapy: ≤6 months, >6 months
- Baseline lactate dehydrogenase (LDH) (normal vs abnormal)
- History of bone marrow involvement (yes vs. no)
- Extra-nodal disease (yes vs. no)

## 6. DEMOGRAPHIC, OTHER BASELINE CHARACTERISTICS AND MEDICATION

### 6.1. Subject Eligibility, Disposition and Protocol Deviations

The subject disposition table will summarize the number of subjects screened, the number and percentage of subjects in each analysis set, the number and percentage of subjects who

discontinued treatment, along with reasons of treatment discontinuation, and the number and percentage of subjects who discontinued study, along with reasons of study discontinuation. The summary tables will be generated separately for all subjects, ITT FL Population, and ITT MZL Population.

Separate by-subject listings will be provided for subject disposition, eligibility, analysis populations, and protocol deviations.

Subject follow-up time (months) on study will be provided in disposition summaries. It is defined as (date of data cutoff – date of first dose + 1) / 30.4375 for patients remaining on study, and (End of Study date – date of first dose + 1) / 30.4375 for patients who discontinued from study.

## **6.2. Demographic and Other Baseline Characteristics**

Descriptive statistics will be presented for continuous variables including age, height, weight, body mass index (BMI) at baseline. The frequency and percentage of subjects will be tabulated for categorical variables including age group (<65 vs. ≥65), sex, child-bearing potential, race, ethnicity, and region of enrollment at baseline. The summary tables will be produced separately for Safety Population, ITT FL Population, and ITT MZL Population.

All demographic data at baseline will be listed.

## **6.3. Baseline Disease Characteristics**

The following baseline disease characteristics will be summarized by treatment group and overall for Safety Population, ITT FL Population, and ITT MZL Population.

- Tumor bulk (largest lymphoid mass <5 cm vs. ≥5 cm, and 7 cm vs. ≥7 cm)
- Disease response to last therapy (relapse vs. refractory)
- Disease response to specific prior cancer therapies (relapse vs. refractory)
  - Anti-CD20 monoclonal antibodies
  - Alkylating agents
  - Bendamustine
  - Immunochemotherapies
- Stage at diagnosis (I, II, III, IV), stage at study entry (I, II, III, IV), and grade at study entry (1, 2, 3a)
- POD24 (yes vs. no)
- Baseline ECOG (0 vs. ≥1)
- Duration of treatment-free interval from the last lymphoma-directed therapy: ≤6 months, >6 months
- Baseline LDH (normal vs abnormal)

Disease response to prior therapy is defined as follows:

- Relapsed disease: disease progression after a response (CR or PR) lasting  $\geq 6$  months

#### **6.4. Refractory Disease: No Response to Therapy (no CR or PR) or Response Lasting <6 months Medical History and Concomitant Diseases**

Medical History will be coded into system organ class (SOC) and preferred term (PT) by Medical Dictionary for Regulatory Activities (MedDRA) Version 21.1 or later. Medical history will be listed but not summarized.

Medical history data listings will be produced.

#### **6.5. Prior and Concomitant Medications**

All prior and concomitant medications and therapies will be recorded from 28 days prior to Cycle 1 Day 1 through 30 days after last dose of ME-401, treatment discontinuation, or until a subsequent anti-cancer therapy is initiated. Medications will be coded by World Health Organization Drug Dictionary (WHO DD) Version Global B3 Sep2018 or later.

Prior medications are medications which stop before the start of study drug. Concomitant medications are medications which start or stop on or after the start of study drug.

For the classification of prior medications vs. concomitant medications, incomplete start or stop dates of medications will be imputed using the algorithm in [Section 5.3.2](#). The medication will be assumed as concomitant if it cannot be definitively shown that the stop date is before the first dose date of study drug.

Prior and concomitant medications will be coded into Anatomical Therapeutic Chemical (ATC) classification levels and preferred term. All prior and concomitant medications will be listed but not summarized.

#### **6.6. Prior Therapies**

The following prior therapies will be summarized using the number and percentage of subjects with each therapy type using Safety Population.

- Prior cancer surgery for follicular lymphoma
- Prior radiotherapy
- Prior transplant
- Prior Cancer therapy
  - Anti-CD20 monoclonal antibodies
  - Alkylating agents
  - Bendamustine
  - Immunochemotherapies
  - Lenalidomide in combination of rituximab

- Number of prior lines of cancer therapies (2 vs. >2)
- Number of prior lines of chemo regimens (1, 2-3, 4+)

The data of prior therapies will also be listed.

## 6.7. Concomitant Procedures

The concomitant medical procedures will be listed but not summarized.

## 7. EFFICACY ANALYSIS

### 7.1. Primary Efficacy Endpoint and Analysis

The primary efficacy endpoint is ORR, defined as the proportion of subjects achieving the best response rating of CR or PR based on the Modified Lugano Classification, assessed by IRRC.

For Primary Analysis and NDA Analysis for FL, ORR will be evaluated by summarizing the number and percentage of subjects with the best overall response (CR/PR) prior to first PD as assessed by IRRC that is reported before the data cutoff date for the Primary Analysis, along with 2-sided 95% exact Clopper-Pearson confidence interval (CI). The primary efficacy analysis will be based on the Primary Efficacy Population for FL (PEP FL).

As a supportive analysis for NDA Analysis for FL, ORR will be analyzed

- using the ITT FL Population by including the PEP FL, ITT IS FL, ITT CS, ITT FL Total patients
- by summarizing the number (percentage) of patients who achieved PR or CR before the data cutoff date for the NDA Analysis for FL submission.

As sensitivity analyses, the above analyses in [Section 7.1](#) will be repeated for EE population and PP population.

All subjects who did not meet the criteria for an objective response by the analysis cut-off date will be considered non-responders.

To evaluate the impact of the covid-19 pandemic on efficacy of ME-401, the above analyses in [Section 7.1](#) will also be conducted using the Modified ITT Population in IS FL patients, i.e., patients who discontinued from treatment early due to covid-19 deaths with no post-baseline efficacy assessment will be excluded from the analysis.

Subgroup analysis of ORR (the proportion of subjects with the best overall response [CR/PR] prior to first PD as assessed by IRRC), that is reported before the data cutoff date for the Primary Analysis, will be performed by the subgroups defined in [Section 5.5](#), based on PEP FL and ITT MZL population. Forest plots will be provided for ORR and 95% CI in selected subgroups.

Waterfall plots of maximum percentage decrease in sum of the products of longest diameters (SPD) measured by the IRRC will be provided for the patients in the PEP FL and ITT MZL population.

## **7.2. Secondary Efficacy Endpoints and Analyses**

### **7.2.1. Objective Response Rate (ORR) by Investigator**

Secondary analysis of the ORR, as determined by the investigator, will be repeated as described above for the analyses of primary efficacy endpoint in [Section 7.1](#).

The concordance in best overall response between IRRC and Investigator assessments will be summarized.

Waterfall plots of maximum percentage decrease in sum of the products of longest diameters (SPD) measured by the investigator will be provided for the patients in the PEP FL and ITT MZL population.

### **7.2.2. Duration of Response (DOR) and Duration of Recaptured Response (DORR)**

DOR is the time from first response (CR or PR) to the time of first PD or the date of death due to any cause (whichever occurs earlier).

For Primary Analysis and NDA Analysis for FL, DOR will be analyzed using the DOR Primary Analysis Set for FL.

As a supportive analysis for NDA Analysis for FL, DOR will be analyzed using the DOR Supportive Analysis Set.

For the Primary and NDA Analysis for MZL, DOR will be analyzed using the DOR Analysis Set for MZL.

Subgroup analysis of DOR using the DOR Primary Analysis Set for FL and the DOR Analysis Set for MZL will be performed by the subgroups defined in [Section 5.5](#).

DORR is the time from recapture of response (CR or PR) to the time of second PD or the date of death due to any cause (whichever occurs earlier).

The assessment of DOR and DORR assessed by IRRC and by Investigator will be summarized separately.

DOR and DORR will be summarized using Kaplan-Meier (KM) summary statistics. The min, max, median duration of response with 95% CI (based on the LOGLOG transformation), number of events, number censored with types of censoring and, KM plot for cumulative probability of DOR and DORR over time will be presented. DOR and DORR will be reported in months. Only subjects who had a response will be included in this summary table, and the denominator will be all subjects in each population who had a documented CR or PR response. Estimates and 95% CIs for DOR rates at 3 months, 6 months, 9 months and 12 months, and, median with 95% CI of the follow-up time (months) based on reverse KM estimate of the DOR time (by reversing the censoring/event status) will be summarized.

KM estimates of DOR will be provided by best response type (CR vs PR).

Forest plots will be provided for median DOR and 95% CI in different subgroups.

### **7.2.3. Complete Response (CR) Rate**

The CR rate is proportion of subjects achieving the best response rating of CR, and will be assessed separately by IRRC and investigator.

For FL Primary Analysis and Final Analysis, the CR rate will include CR prior to first PD that is reported before the data cutoff date for Primary Analysis.

As a supportive analysis in Final Analysis, CR rate will be summarized by including CR achieved that is reported before the data cutoff date for NDA Analysis for FL.

For CR rate, the number and percent (%) of subjects with 2-sided 95% exact Clopper-Pearson CIs will be summarized for subjects in PEP FL, ITT MZL population, ITT FL population (for NDA Analysis for FL only), EE population, and PP Population.

### **7.2.4. Progression Free Survival (PFS)**

PFS is the time from first dose of study drug until first disease progression or death from any cause. The analysis of PFS will be performed based on the assessment by IRRC and investigator, separately.

PFS will be summarized using Kaplan-Meier summary statistics for PEP FL, ITT MZL population, and ITT FL population (for NDA Analysis for FL only). The min, max, and median PFS with 95% CI (based on the LOGLOG transformation), number of events, number censored with types of censoring, and KM plot for cumulative probability of PFS over time will be presented. PFS will be reported in months. Estimate and 95% CI for PFS rates at 6 months, 12 months, 18 months and 24 months, and median with 95% CI of the follow-up time (months) based reverse KM estimate of the PFS time (by reversing the censoring/event status) will be summarized.

KM estimates of PFS will be provided by best response type (CR, PR and non-responders).

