**Figure 1: Study Schema**

a. Screening from Day -28 to Day -1.

b. IS dosing schedule: 60 mg daily for the first 2 cycles (56 days) followed by 60 mg daily for 7 days of every 28-day cycle (7 days on / 21 days off treatment).

c. Follow-up Period will include: 1) EOT/30-Day Safety Follow-up visit will occur 30 ( $\pm 3$ ) days from the last day of study drug treatment. 2) Efficacy Follow-up - for subjects who discontinue study treatment due to reasons other than disease progression or death, response follow up will occur until PD or the start of a new anti-cancer therapy. 3) Survival Follow-up visits will occur every 3 months until death, and will continue for up to 3 years after the last subject is enrolled in the study.

d. Response assessments will be performed every 2 months ( $\pm 7$  days) for the first 6 months, every 3 months ( $\pm 7$  days) during the following 12 months, and every 6 months ( $\pm 14$  days) thereafter (starting with month 18).

Abbreviations: CS = continuous schedule; EOT = End of Treatment; FU = follow up; IS = intermittent schedule; PD = progressive disease.

For subjects who experience hematologic or non-hematologic adverse reactions, please refer to ME-401 toxicity management ([Table 4](#)) and modified dosing schedules in [Section 5.3.1](#).

ME-401 is provided as 60 mg capsules. ME-401 is to be taken orally once a day at approximately the same time each day in accordance with the IS regimen (or CS dosing regimen if switched from IS after PD).

Subjects must receive prophylaxis treatment for *Pneumocystis jirovecii* pneumonia (PJP) as prescribed within this protocol (see [Section 5.4.3](#)).

See the Schedule of Assessments ([Appendix 1](#)) for a detailed list of study procedures.

The Modified Lugano 2014 criteria will be used for response assessment ([Appendix 5](#)). The Investigator's assessment of disease response will be used for subject management. For the primary analysis, disease/response assessment will be performed by an IRRC blinded to Investigator assessment and treatment assignment. Methods for disease/response assessment by the IRRC are described in the IRRC Charter. Disease/response assessment will occur every 2 months for the first 6 months, every 3 months during the next 12 months, and every 6 months thereafter.

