#### **1.6.2.4. Efficacy**

The efficacy analysis is based on 28 April 2019 data-cut off and is focused on subjects with relapsed or refractory FL and CLL/SLL. The Efficacy analysis set included 64 subjects who had at least one response assessment after baseline and included 50 subjects with FL and 14 subjects with CLL/SLL. The ORR was 80% for subjects with FL and 100% for subjects with CLL/SLL. There was no significant difference in response between subjects who received ME-401 as a single agent or in combination with rituximab, and no significant difference between treatment schedules (CS vs IS). Among all the subjects achieving a partial response (PR) or CR, the responses occurred rapidly for the majority of subjects (48/54, 89%), with response being assessed after the first 2 cycles of therapy. Median duration of response (DOR) for the IS group is 11.2 months, with a median (IQR) -follow up time on study of 8.8 (4.9–12.0) months. The median DOR for the CS group has not been reached, with a median (IQR) follow-up time on study of 8.3 (4.6–17.5) months. Updated data on efficacy and safety of ME-401 from the ongoing Phase 1b study is presented in [Section 2.3](#).

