For subjects who experience hematologic toxicity; diarrhea/colitis, cutaneous reactions (including rash and mucositis), AST/ALT elevation, or non-infectious pneumonitis (NIP); or other toxicities, refer to ME-401 toxicity management (Table 4) and modified dosing schedules in [Section 5.3.1](#). Study treatment interruption is acceptable due to observed adverse reactions, and is allowed for up to 6 continuous weeks from drug interruption. Once a subject has recovered from a toxicity, treatment may be resumed beginning at Day 1 of the subsequent cycle of therapy according to the toxicity management indicated in [Table 4](#).

Study drug administration, study visits, and protocol-mandated assessments are conducted in 28-day cycles. Subject participation in the study is expected to be approximately 3–4 years, including 28 days for screening, 18 months of dosing with study drug, and up to 3 years of follow-up for survival after discontinuation of study drug. This is an estimated average duration of subject participation; actual duration may be shorter or longer based on disease response, tolerability to therapy, and duration of the long-term follow-up period.

Disease/response assessments utilizing diagnosis quality scans (CT scan with contrast, diagnostic quality PET/CT scan) will be initially performed at screening, after 4 months and 12 months on therapy, and at any time to confirm CR. Once a CR has been documented, F-fluorodeoxyglucose (FDG)-PET scan is no longer required to monitor disease response and a CT scan is an appropriate imaging test. CT scans will be performed at all other protocol

prespecified timepoints for disease/response assessment. The disease/response assessment will be performed every 2 months ( $\pm 7$  days) for the first 6 months on study, every 3 months ( $\pm 7$  days) during the following 12 months, and every 6 months ( $\pm 14$  days) thereafter.

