### **3. ENDPOINTS**

#### **3.1. Primary Efficacy Endpoint**

The primary efficacy endpoint is ORR, defined as the proportion of subjects achieving the best response rating of CR or PR based on the Modified Lugano Classification (response criteria summarized in [Appendix 5](#) of Protocol Amendment 2), as determined by IRRC.

For both Primary Analysis and NDA Analysis for FL, ORR will include best response of PR and/or CR prior to first PD that is reported before the data cutoff date for FL Primary Analysis, among all patients in the Primary Efficacy Population in FL (PEP FL).

As supportive analyses for NDA Analysis for FL, ORR will be summarized by 1) including PR or CR achieved that is reported before the data cutoff date for NDA Analysis for FL, among all patients in the Primary Efficacy Population in FL; 2) including PR or CR achieved that is reported before the data cutoff date for NDA Analysis for FL, among all patients in the ITT FL Population.

Time to response will be assessed to provide supportive information for the primary endpoint of ORR. It is defined as the time from the first dose of study drug to the first objective response for the subjects who achieved best response of CR or PR.

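### Kaplan-Meier curves of PFS from first dose, split by later best response, carry guarantee-time bias and can show a large gap even if response is uninformative

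*SAP*

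**What the plan says.** SAP 7.2.4 gives the time origin: "PFS is the time from first dose of study drug until first disease progression or death from any cause". It then plans: "KM estimates of PFS will be provided by best response type (CR, PR and non-responders".

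Three other provisions fix who falls in each group:

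- SAP 3.1 bases the primary ORR on "best response of PR and/or CR prior to first PD that is reported before the data cutoff date for FL Primary Analysis". SAP 7.2.4 does not restate the rule for the PFS display, so I take this primary definition to apply.
- SAP 7.1 adds: "All subjects who did not meet the criteria for an objective response by the analysis cut-off date will be considered non-responders".
- The protocol synopsis sets response assessments "every 2 months for the first 6 months, every 3 months during the next 12 months". The schedule of assessments puts the first three scans on Days 61, 121 and 182, each ±7 days. Under Protocol 5.1, PET follows "after 4 months and 12 months on therapy, and at any time to confirm CR".

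SAP 7.2.2 plans a related display: "KM estimates of DOR will be provided by best response type (CR vs PR". DOR there starts at first response.

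Neither document provides a landmark, a time-dependent treatment of response or a caution on interpretation. No test or hypothesis is attached to either display.

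**The concern.** The PFS curves start on Day 1, but subjects are sorted by something that happens afterwards. To be a responder, a subject must reach a scan without progression and be rated CR or PR there. No responder can have an event before that scan. A subject who progresses or dies by the first scan has no chance to respond and is counted as a non-responder. The two curves must therefore separate early, whatever the true relation between response and progression.

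This is a single-arm trial with response as its primary endpoint, and the SAP is written to support a marketing application. Side-by-side curves invite the reading that responders do better because they responded. The display cannot separate any real prognostic value of response from the effect of the grouping.

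**Working it through.** **No planned figure to reproduce for this display.** The documents give no PFS assumption. The FL sample size does reproduce: at least 54 responses of 91 gives exact one-sided alpha 0.0196 at 48% and power 0.910 at 65.5%. The point below does not touch it.

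**Inputs from the documents.** Scan days are 61, 121, 182, 274, 365 and so on (schedule of assessments). Protocol 1.6.2.4 says of Phase 1b that "the responses occurred rapidly for the majority of subjects (48/54, 89%), with response being assessed after the first 2 cycles of therapy".

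**Assumptions.** Exponential PFS with median 9 to 18 months. A probability of 75–80% of responding if still event-free. A share of 70–89% of responders identified at the first scan. Response is drawn independently of progression, so the true gap is zero.

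**Hand calculation (12-month median, 80% response probability, every response at Day 61).** Let S(t) = 2^(−t/365.25).

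- S(61) = 0.891, S(121) = 0.795, S(365) = 0.500.
- Responders at 12 months: S(365)/S(61) = 0.500/0.891 = 56.2%.
- Non-responders: (1 − 0.80) × S(365) / [1 − 0.80 × S(61)] = 0.100/0.287 = 34.8%.
- False gap: 21.4 points, although everyone shares a true 50%.

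**Simulation.** 400,000 subjects per setting, with progression detected at the next protocol scan. Responses not found at Day 61 are spread over Days 121 to 365, which widens the gap.

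| Median PFS (months) | Found at first scan | Response probability | Responders, 12-month PFS | Non-responders, 12-month PFS | Gap (points) |
|---|---|---|---|---|---|
| 9 | 89% | 80% | 47.6% | 23.8% | 23.8 |
| 9 | 70% | 80% | 50.0% | 21.5% | 28.5 |
| 12 | 89% | 75% | 57.4% | 36.3% | 21.1 |
| 12 | 89% | 80% | 57.6% | 32.9% | 24.7 |
| 12 | 70% | 80% | 59.8% | 30.2% | 29.6 |
| 16 | 89% | 80% | 65.9% | 42.7% | 23.2 |
| 18 | 89% | 75% | 69.2% | 49.7% | 19.5 |

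**By category.** For a 12-month median, 89% at the first scan and 80% response probability, I also assumed that 30% of potential responders reach CR, 60% of them at Day 121 and 40% at Day 365. Twelve-month PFS is then 74.5% for CR, 52.5% for PR and 32.9% for non-responders. CR gains most because it can be recorded later.

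**Where the gap comes from.** At a 12-month median and 80% response probability, I removed subjects with progression by the Day 61 scan from the non-responders. With 89% of responders found at the first scan, the gap falls from about 25 points to about 6. With 70%, it falls from about 30 to about 15. At the Phase 1b timing, first-scan failures are the main source; with slower responses they account for about half.

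**Landmark check.** Take subjects event-free at Day 121, group them by response status then, and read at Day 365. The expected value is S(365)/S(121) = 0.500/0.795 = 62.9% in both groups. The simulation gives 63.1% against 62.8%. Across all settings the landmark gap is about 0.5 points or less.

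**Share excluded at Day 121**, 1 − S(121): 26.4%, 20.5% and 14.2% for medians of 9, 12 and 18 months. That is about 13 to 24 of the 91 FL subjects, or about 5 to 8 of the 32 MZL subjects.

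**The case against.** The strongest reply is that this is one descriptive figure. SAP 7.2.4 attaches no test, hazard ratio or claim to it, and Table 4 of the SAP does not list it as a separate analysis. It leaves the ORR test, the sample size and overall PFS alone. All of that stands, and it limits the weight of the point.

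A second reply is that most of the gap at the Phase 1b response timing comes from early progressors, and that counting them as non-responders is correct for ORR. That is also true. It is right for a response rate, but it does not make the same grouping suitable for a time-to-event curve starting at Day 1.

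Two stronger readings are tempting and are not supported:

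- A reader might infer that the gap in the real data will be largely an artefact. The simulation fixes the true association at zero, so its whole gap is artefact by design. It shows what the method could produce alone, not what share of an observed gap it would explain. Response may well have real prognostic value.
- A reader might infer that the DOR split by CR and PR has the same flaw to the same degree. DOR starts at first response, so only a later conversion from PR to CR brings guaranteed time. That bias is smaller, and it has not been quantified here.

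A landmark also has drawbacks. It leaves out early failures, and a CR first documented after Day 121, for example at the 12-month PET, stays in the group held at Day 121.

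**Conclusion.** The point holds as a low-cost improvement to a descriptive display. The direction of the bias follows from the SAP's own definitions and needs no assumption. Its size does: about 19 to 30 points at 12 months under no true association, and for a 12-month median about 57–60% in responders against 30–36% in non-responders. Median PFS, response timing in this trial, the response probability and the CR timing are all assumed. A Day 121 landmark removes the false gap, giving about 63% in each group at a 12-month median. No primary conclusion of the trial depends on this display.

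**What to change.** In SAP 7.2.4, replace or accompany the best-response curves with a pre-specified landmark analysis:

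- Group by response status (CR, PR, none) at the Day 121 scan, which is already a scheduled CT and PET visit. State how scans within its ±7-day window are handled.
- Include only subjects event-free and under follow-up at the landmark, and measure PFS from Day 121.
- Keep subjects who respond or deepen their response later in their landmark group.
- Report the number excluded (about 14–26% under the assumptions above).

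If the best-response curves are kept, add a footnote that they do not support an inference that response prolongs PFS.

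For DOR by CR and PR in SAP 7.2.2, either add the same kind of footnote or group by response category at the landmark among subjects still in response, with time measured from the landmark. Subjects whose first response comes later are then outside that display, and their number should be given.

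The cost is a little programming and no new data. The price is a smaller descriptive sample, felt most in the MZL cohort.
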